10.3 Recording of (Serious) Adverse Events

Clinical investigators and ultimately the protocol Principal Investigator (PI) have the primary responsibility for AE identification, documentation, grading, and assignment of attribution to the investigational agent/intervention.

Clinical study subjects will be routinely questioned about AEs at study visits. The well-being of the subjects will be ascertained by neutral questioning ("How are you?"). The investigator is responsible for reporting all AEs occurring during the course of the study.

All observed or volunteered adverse drug events (serious or non-serious) and abnormal test findings, regardless of treatment group or suspected causal relationship to the investigational drug or study treatment(s) will be recorded in the patient file and subsequently in the eCRF.

All SAEs, will be fully documented in the appropriate eCRF. For each SAE, the investigator will provide the onset, duration, intensity, treatment required, outcome and action taken with the investigational product.

The intensity of SAEs will be assessed as being

- mild (hardly noticeable, negligible impairment of well-being),
- moderate (marked discomfort, but tolerable without immediate relief), or
- severe (overwhelming discomfort, calling for immediate relief).

The investigator will determine the relationship of the investigational drug to all AEs as defined on the AE page of the eCRF.

10.4 Assessment of Causality (Serious) Adverse Events

The assessment by the investigator with regard to the study drug relation is done according to the following definitions:

Relationship	Description
Definitely	Temporal relationship Improvement after dechallenge* Recurrence after rechallenge (or other proof of drug cause)
Probably	Temporal relationship Improvement after dechallenge No other cause evident
Possibly	Temporal relationship Other cause possible
Unlikely	Any assessable reaction that does not fulfil the above conditions
Not related	Causal relationship can be ruled out
*Improvement after dechallenge only taken into consideration, if applicable to reaction	

10.5 Reporting of Serious Adverse Events

All SAEs must be reported immediately and within a maximum of 24 hours to the Sponsor-Investigator of the study. The Sponsor-Investigator will re-evaluate the SAE and return the form to the site.

The Sponsor-Investigator is responsible for SAE reporting to the IEC, according to the following details:

- Reporting to IEC any SAE which resulted in death:
 - **without delay**, and no later than **7 calendar days**.
- Reporting to IEC of fatal and life-threatening SAEs if evaluated as “drug related” (SADR):
 - **without delay** and no later than **7 calendar days** following awareness that event meets criteria for an SADR.
- Reporting to IEC of fatal and life-threatening SAEs if evaluated as “suspected”, “unexpected” and “drug related” (SUSAR)
 - **without delay** and no later than **7 calendar days** following awareness that event meets criteria for an SUSAR.
 - follow-up information regarding the SUSAR within **further 8 calendar days**.
- Reporting to IEC of non-fatal and not life-threatening SAEs if evaluated as “suspected”, “unexpected” and “drug related” (SUSAR):
 - **promptly** and no later than **15 calendar days** following awareness that event meets criteria for a SUSAR.
- All other SAEs will be summed up in the **annual safety update report**. The annual safety report contains information from all sites including information from all sites. The Sponsor-Investigator prepares it, and then submits it to the participating Investigators. The participating Investigators submit it to the local committees

The Sponsor-Investigator is responsible for SAE reporting to Swissmedic according to the following details:

- Compliance with the regulatory requirements of Swissmedic regarding prompt reporting of unexpected SAEs for which a causal relationship with the study drug or device cannot be ruled out.
- Reporting to Swissmedic of fatal and life-threatening SAEs if evaluated as “suspected”, “unexpected” and “drug related” (SUSAR):
 - **without delay** and no later than **7 calendar days** following awareness that event meets criteria for a SUSAR;
 - follow-up information regarding the SUSAR within **further 8 calendar days**.
- Reporting to Swissmedic of non-fatal and not life-threatening SAEs if evaluated as “suspected”, “unexpected” and “drug related” (SUSARs):
 - **promptly** and no later than **15 calendar days** following awareness that event meets criteria for a SUSAR.
- Sending yearly safety reports, starting one year after the date of notification to Swissmedic. These reports should contain:
 - A concise critical summary of the safety profile of the drug studied as well as the safety issues that have arisen;
 - A listing of all SUSARs that have occurred in Switzerland and at international level (if applicable);

- Ideally all adverse drug reactions at international level.
- The accompanying letter provided with the Annual Safety Report should contain a short summary of the status of the clinical trial in Switzerland (number of centers open/closed, number of patients recruited/recruitment closed, and number of SAR/SUSAR).

An unexpected SAE refers to any AE, the nature or severity of which is not consistent with the applicable product information (see Appendix)

10.6 Follow up of (Serious) Adverse Events

Subjects terminating the study (either regularly or prematurely) with

- reported ongoing SAE, or
 - any ongoing SAEs of laboratory values or of vital signs being beyond the alert limit
- will return for a follow-up investigation. This visit will take place up to 30 days after terminating the treatment period. Follow-up information on the outcome will be recorded on the respective AE page in the eCRF. All other information has to be documented in the source documents. Source data has to be available upon request.

In case of subjects lost to follow-up, efforts should be made and documented to contact the subject to encourage him/her to continue study participation as scheduled. In case of minor AEs a telephone call to the subject may be acceptable.

All new SAE or pregnancies that the investigators will be notified of within 30 days after discontinuation of study medication have to be reported in appropriate report forms and in the eCRF if required.

Follow-up investigations may also be necessary according to the investigator's medical judgment even if the subject has no AE at the end of the study. However, information related to these investigations does not have to be documented in the eCRF but must be noted in the source documents.

11. DATA QUALITY ASSURANCE

The Sponsor-Investigator is implementing and maintaining quality assurance and quality control systems with written SOPs and Working Instructions to ensure that trials are conducted and data are generated, documented (record), and reported in compliance with the protocol, GCP, and applicable regulatory requirement(s).

Monitoring and Audits will be conducted during the course of the study for quality assurance purposes.

11.1 Routine Monitoring

Regular monitoring visits at the investigator's site prior to the start and during the course of the study will help to follow up the progress of the clinical study, to assure utmost accuracy of the data and to detect possible errors at an early time point. The Sponsor-Investigator organizes professional independent monitoring for the study.

All original data including all patient files, progress notes and copies of laboratory and medical test results must be available for monitoring. The monitor will review all or a part of the eCRFs and written informed consents. The accuracy of the data will be verified by reviewing the above referenced documents.

11.2 Audits and Inspections

A quality assurance audit/inspection of this study may be conducted by the regulatory authority or IEC, respectively. The quality assurance auditor/inspector will have access to all medical records, the investigator's study related files and correspondence, and the informed consent documentation that is relevant to this clinical study.

The investigator will allow the persons being responsible for the audit or the inspection to have access to the source data/documents and to answer any questions arising. All involved parties will keep the patient data strictly confidential.

11.3 Specification of Source Documents

The following documents are considered source data, including but not limited to:

- SAE worksheets
- Nurse records, records of clinical coordinators, and
- Medical records from other department(s), or other hospital(s), or discharge letters and correspondence with other departments/hospitals, if subject visited any during the study period and the post study period.

Source data must be available at the site to document the existence of the study subjects and substantiate the integrity of study data collected. Source data must

include the original documents relating to the study, as well as the medical treatment and medical history of the subject.

The following information (at least but not limited to) should be included in the source documents:

- Demographic data (age, sex)
- Inclusion and Exclusion Criteria details
- Participation in study and signed and dated Informed Consent Forms
- Visit dates
- Medical history and physical examination details
- Key efficacy and safety data (as specified in the protocol)
- AEs and concomitant medication
- Results of relevant examinations
- Laboratory printouts
- Dispensing and return of study drug details
- Reason for premature discontinuation
- Randomization number

12. STATISTICS

12.1 Statistical and Analytical Plans

This is a multicentric randomized controlled trial comparing the effect of 2 different anesthetic regimens (sevoflurane *versus* propofol) on perioperative levels of CTC in patients undergoing surgery for primary breast cancer.

Using a strict 4 time-points schedule, the number of CTC in peripheral blood will be measured before and after exposition to general anesthesia (primary outcome).

Using a mixed model analysis, the effect of two independent variables on the mean level of CTC will be explored: a within-subject time factor (i.e. variation of CTC levels over time) and a between-subject treatment factor (i.e. anesthesia regimen).

Fixed randomization based on a 1:1 allocation ratio will be performed using minimization (www.randomizer.at). Patients will be stratified according to their ASA class during the randomization process, which will be performed using a web-based interactive allocation platform (www.randomizer.at).

Accordingly, the risk of allocation and selection bias will be negligible. Restriction and stratified randomization are likely to minimize the risk of unbalanced known and unknown confounders. Blinding of participants and outcome assessors (laboratory staff, pathologist) will prevent measurement/detection bias.

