6. STUDY DESIGN

6.1 General Design

We will conduct a prospective, randomized, double blinded, controlled study over a period of 52 months. We will consider adult female patients undergoing surgery for primary breast cancer. Expecting a dropout rate of 10% over time, we will recruit a total of 232 patients (i.e. 116 in each study group).

Patients will be screened for eligibility according to the inclusion and exclusion criteria on the day prior to surgery. Written informed consent will be subsequently obtained. A pregnancy test will be performed for all included patients.

On the day of operation, the patients will be premedicated with midazolam *per os* (3.75mg to 7.5mg). Randomization will be performed according to a computer-generated anesthesia-assignment (www.randomizer.at) once the patient will be installed for induction of anesthesia. By this means, concealment of random allocation will be ensured.

After preoxygenation, induction of anesthesia will be administrated in both groups similarly, using fentanyl 2-3mcg/kg, Pentothal 4-6 mg/kg and rocuronium 0.6mg/kg intravenously. Maintenance of anesthesia will be conducted following the assignment group:

1) in “Group Sevo”, anesthesia will be maintained with sevoflurane in 80% oxygen, adjusted to keep an adequate depth of anesthesia (minimal alveolar concentration (MAC) between 0.8 and 1.2), attested by bispectral (BIS) index values between 40 and 60.

2) in “Group Propofol” anesthesia will be maintained with a target-controlled infusion (TCI) device providing an intravenous propofol dose adjusted to keep an adequate depth of anesthesia (TCI values: start after induction with 2.0mcg/ml, then ranging from 3.0mcg/ml to 5.0mcg/ml), attested by BIS index values between 40 and 60.

Patients will be ventilated with 80% oxygen in air.

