6.2 Primary Study Endpoint: blood CTC levels

The primary endpoint, blood CTC levels, will be assessed at 4 pre-defined time points using the CellSearch® approach: two 7.5ml samples of blood will be collected pre-operatively (visit 2, before induction of anesthesia), at the end of surgery (visit 3, before extubation) and two times postoperatively (visit 4, 48h postoperative, and visit 5, 72h after surgery, before hospital discharge). The number of CTC per 7.5ml of peripheral blood will be determined by the CellSearch® system within 96 hours of blood collection. The analysis will account for the effect of repeated measurements over time (within-subject factor) and the effect of anesthesia regimen (between-subject factor) as described under section 12.

The CellSearch® approach

The CellSearch® assay contains a ferro fluid-based capture reagent and immunofluorescent reagents. The ferrofluid reagent consists of particles with a magnetic core surrounded by a polymeric layer coated with antibodies targeting the epithelial cell adhesion molecule (EpCAM) antigen for capturing CTC. After immunomagnetic capture and enrichment, fluorescent reagents (anti-CK-phycoerythrin, DAPI, and anti-CD45-allophycocyanin) are added for identification and enumeration of CTC. (www.veridex.com)

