8.2 Method of Assigning Subjects to Treatment Groups

Fixed randomization based on a 1:1 allocation ratio will be performed. Balanced treatment allocation will be ensured using block sizes of 4. Patients will be stratified according to their ASA class during the randomization process, which will be performed using a web-based interactive allocation platform (www.randomizer.at).

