8.4 Prior and Concomitant Therapy

Patients being on any systemic immunosuppressive therapy (glucocorticoids, cytostatics, antibodies, drugs acting on immunophilins, interferon, TNF bindings proteins, mycophenolate), as well as patients taking chronically opioids, planned for pre-operative chemo- or radiotherapy, or undergoing surgery with concomitant

regional anesthesia (epidural catheter, paravertebral blockade, wound infiltration with local anesthetics) will not be included, as these factors are known to interfere with the immune system.^{84,88,89}

Of note is that patients undergoing *intraoperative* radiotherapy with Intrabeam immediately after removal of the tumor are included. This is a new localized intraoperative “standard of care” therapy in breast cancer.

Long-term medications, such as beta-blockers or COX-inhibitors, as well as perioperative blood transfusion or postoperative opioids, have also been suggested to affect the immune system.^{84,87} However, because the benefits of these treatments outweigh their presumable detrimental effect on the immunity, and because strict avoidance of opioids in the postoperative phase would lead to increased pain and distress, these treatments will not be interrupted nor avoided. Opioids will be administered following a strict protocol mentioned previously (8.4.2.1). Adjustment for residual confounders will be performed at the analytical level.

All concomitant and/or rescue treatment(s) have to be recorded in the eCRF, except for perioperative standard medication such as prophylactic antibiotics or heparin.

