12.3.1 Primary Analyses

The primary endpoint, i.e. blood CTC levels, is a continuous variable. In our study, 2 independent variables may interact with CTC levels: a time factor, which results from repeated measurements over time (i.e. within-subjects factor) and an intervention factor, which is the anesthesia regimen (between subjects factor). Thus, our primary analysis will be performed using a linear mixed model with random effects matrix to account for within-subjects correlated observations as indicated for longitudinal data analysis.

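### Sections 8.2 and 12.1 name different allocation methods, and ASA class stratifies the randomisation but is not in the primary model as described

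*Protocol*

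**What the plan says.** **Allocation.** Section 8.2 describes fixed 1:1 randomisation on a web platform, in which "Patients will be stratified according to their ASA class during the randomization process", and adds that "Balanced treatment allocation will be ensured using block sizes of 4". Section 12.1 describes the same 1:1 allocation, stratified by the same factor on the same platform, but says that the "1:1 allocation ratio will be performed using minimization". Section 6.1 places randomisation at the moment "once the patient will be installed for induction of anesthesia".

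**Primary model.** Section 12.1 says that, in a mixed model, "the effect of two independent variables on the mean level of CTC will be explored", and names a within-subject time factor and a between-subject treatment factor. Section 12.3.1 repeats the count ("In our study, 2 independent variables may interact with CTC levels") and derives from it a linear mixed model with random effects. Section 6.2 names the same two factors for the primary endpoint. No section places ASA class in the model. Section 7.1 admits ASA I to III, and Table 4 lists ASA class among the data collected.

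**The concern.** The allocation statements cannot both be true. Permuted blocks follow a list generated in advance within each stratum. Minimization assigns each patient from the imbalance accumulated so far. Section 12.1 goes straight on to conclude that allocation and selection bias will be negligible, and section 8.6 says that the anaesthesiologist responsible for randomisation cannot be blinded. A reader who wants to judge that conclusion, or an author who has to report the method, needs to know which one was used.

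The model description raises a different matter. Stratifying on a factor removes chance imbalance in it between the arms. If the factor predicts the outcome and is then left out of the model, the variation it explains stays in the error term although the design has already balanced it. The reported standard error is then larger than the true sampling error of the treatment difference. At stake is a little precision and power that the design has already secured.

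**Working it through.** **1. Allocation.** No arithmetic applies.

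| | Section 8.2 | Section 12.1 |
|---|---|---|
| Ratio | 1:1 | 1:1 |
| Stratified by | ASA class | ASA class |
| Platform | web system | same web system |
| Method | blocks of 4 | minimization |

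Everything agrees except the method.

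**2. The protocol's sample size (section 12.5).** Inputs: effect 0.3, within-subject correlation 0.4, two-sided 5%, power 80%, dropout 10%.

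- One measurement per patient: 2 × ((1.960 + 0.842)/0.3)² = 174.4 per arm.
- Mean of m equally correlated measurements: multiply by (1 + (m − 1) × 0.4)/m. For the three postoperative visits this is 1.8/3 = 0.60, giving 174.4 × 0.60 = 104.7.
- Dropout: 104.7/0.9 = 116.3, against the stated 116.

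The protocol does not state m or the correlation structure. With m = 4 the result is 174.4 × 0.55/0.9 = 106.6, so m = 3 is the closer reading and is used below as an assumption.

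**3. Cost of leaving ASA class out.** Take 104 patients per arm (116 × 0.9 = 104.4), V = 0.60 and SE = √(2 × 0.60/104) = 0.1074. Let R² be the share of the variance of the patient mean explained by ASA class. The protocol gives no value, so a range is assumed. With ASA class balanced by design, the true standard error is SE × √(1 − R²), whereas the model without ASA class reports SE. Hence:

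- SE ratio, without/with ASA class = 1/√(1 − R²)
- Type I error without = 2 × (1 − Φ(1.96/√(1 − R²)))
- Power without = Φ((0.3/SE − 1.96)/√(1 − R²))
- Power with = Φ(0.3/(SE × √(1 − R²)) − 1.96)

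| Assumed R² | SE ratio | Type I error without | Power without | Power with | Loss (points) |
|---|---|---|---|---|---|
| 0 | 1.000 | 0.050 | 79.8% | 79.8% | 0 |
| 0.02 | 1.010 | 0.048 | 80.0% | 80.5% | 0.5 |
| 0.05 | 1.026 | 0.044 | 80.4% | 81.7% | 1.4 |
| 0.10 | 1.054 | 0.039 | 81.0% | 83.7% | 2.7 |

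With all four visits (V = 0.55, SE = 0.1028) the losses are 0, 0.5, 1.2 and 2.4 points.

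**4. Does the allocation method change this?** A simulation used 208 patients, assumed ASA I/II/III shares of 30/50/20%, and 20,000 runs (Monte Carlo standard error 0.0015). Type I error without ASA class, at R² of 0, 0.02, 0.05 and 0.10, was:

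- blocks of 4: 0.049, 0.050, 0.044, 0.040
- minimization with an assumed 0.8 biased coin: 0.053, 0.044, 0.047, 0.037

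With ASA class in the model it lay between 0.047 and 0.053. Both methods lead to the same conclusion.

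**5. Treatment-by-time contrast.** An ASA effect that is constant over visits cancels from differences within a patient. With complete data the SE ratio is exactly 1. With 10% of postoperative visits missing it differs from 1 by less than 0.1%.

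**The case against.** The best defence concerns the model. Covariates of a mixed model are often left to the analysis plan, which is not shown. The protocol's two variables can be read as the effects of interest rather than a full list of terms, and nothing forbids an ASA term. This largely stands: the text does not prove that the final analysis omits ASA class, and a reader who infers that goes too far. What remains is that three sections describe the model, two of them count its factors, and none mentions the factor used to stratify.

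It is also fair that every loss figure depends on an assumed R² and on a between-arm contrast of means, which the protocol does not define precisely. If ASA class barely predicts CTC, or if the test is treatment by time, almost nothing is lost.

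On allocation, the defence is that minimization may be a slip, because section 12.1 also calls the scheme fixed and stratified, which suits blocks better. That may be so, but the contradiction remains, and an analysis plan would not remove it from the protocol.

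Three stronger readings are not supported.

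- **Inflated false-positive rate.** A reader might infer this from the omission of ASA class. The effect runs the other way.
- **Compromised allocation.** The documents show two descriptions, not a failure. Consent is obtained the day before surgery and assignment is made only at induction.
- **A conflict over confounders.** Section 8.4 says that long-term medications, "as well as perioperative blood transfusion or postoperative opioids, have also been suggested to affect the immune system", and then promises adjustment for residual confounders. Sections 5.2.3 and 12.3.2 make such adjustment exploratory and as needed. Section 8.4 is a general pointer compatible with those specifics, and section 5.2.3 itself lists hypothermia and transfusion among the variables collected for that purpose.

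**Conclusion.** Minor, in two parts. The conflict over the allocation method is certain from the text. It has no numerical effect on the primary estimate, but the method cannot be reported correctly until it is resolved. The absence of ASA class from the described model is a small and avoidable inefficiency. It causes no bias in the linear model, and its largest cost in the range examined is 2.7 points of power, at an assumed R² of 10%. That size rests on 104 analysed patients per arm, equal correlation of 0.4, the mean of three postoperative visits and near-perfect balance on ASA class. The sample size is not in question.

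**What to change.** 1. Make sections 8.2 and 12.1 state the one allocation method actually set in the web system, with its parameters. This changes wording only.
2. In sections 6.2, 12.1 and 12.3.1, add ASA class as a fixed effect in the primary linear mixed model, or confirm that the analysis plan already does so. With ASA I to III this costs two degrees of freedom. ASA class is already collected, and the total stays at 232.
3. If ASA class is also added to the logistic mixed model of section 12.3.2, say that the odds ratio is then conditional on ASA class.
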